10.3 Safety Laboratory Variables

Baseline for all laboratory analyses will be the values obtained at the last assessment prior to the first dose of the IMP. Treatment-emergent laboratory data will include tests completed after the first dose of IMP. End of treatment will include the last post-baseline observation during the treatment period.

Laboratory variables will be grouped under “Haematology”, “Coagulation”, “Serum chemistry” or “Urinalysis”

10.3.1 Summary Statistics

Change and percentage change from baseline at end of treatment will be presented for each laboratory variable. In addition, descriptive statistics, i.e., the number of subjects with data, mean (standard deviation), median, minimum, and maximum values, will be presented for observed values and change/percentage change from baseline at baseline, Week 2, Months 2, 4, and 6 for each laboratory variable. The Week 2, Months 2, 4, and 6 measurements for the analysis will be identified based on the method described in Section 9.1.

10.3.2 Laboratory Variable Changes Relative to Normal Range

A shift table regarding the laboratory value category defined below will be created for baseline and end of treatment for each laboratory parameter.

- Low: Values which are below the lower reference range limit;
- Normal: Values which are within the lower and upper reference range;
- High: Values which are above the upper reference range limit.
- Absent: No value for measured variable (for urinalysis only)
- Present: Any value obtained for measured variable (for urinalysis only)

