7.1.7 Clinical Laboratory Variables

Hematology, Serum Chemistry, and Urinalysis

Safety hematology, coagulation and serum chemistry tests will be performed at Visit 0 (screening, Pathway 3 - *de novo* only), Visit 2 (Week 2), and Visit 5 (Month 6) or at early withdrawal. Standard urinalysis will be performed at Visit 0 (screening, Pathway 3 - *de novo* only) and Visit 5 (Month 6) or at early withdrawal.

Hematology: hematocrit, hemoglobin, platelet count, red blood cell count, white blood cell count, and differential count

Coagulation: prothrombin time (measured as international normalized ratio), activated partial thromboplastin time

Serum chemistry: glucose, blood urea nitrogen, creatinine, creatinine clearance (via estimated glomerular filtration rate [eGFR]), potassium, sodium, chloride, calcium, total protein, albumin, total bilirubin, alkaline phosphatase, aspartate aminotransferase, alanine aminotransferase, and gamma glutamyl transferase

Urinalysis: leukocyte, blood, pH, specific gravity, nitrite, protein, glucose, urobilinogen, and microscopic if positive for blood, leucocytes, and nitrite

The investigator will review the laboratory results and evaluate and document whether the results are normal or abnormal and whether abnormal results are clinically significant. The laboratory report will be signed and dated by the investigator.

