8 ADVERSE EVENTS

8.1 Adverse Event Definition

An AE is any untoward medical occurrence in a subject participating in a clinical trial. It includes:

- any unfavorable and unintended sign, symptom or disease temporally associated with the use of the IMP, whether or not considered to be caused by the IMP
- AEs commonly observed and AEs anticipated based on the pharmacological effect of the IMP
- any laboratory abnormality, vital sign, or finding from physical (or gynecological) examination assessed as clinically significant by the investigator (note: findings from assessments and examinations done during screening are not AEs, but are recorded as medical history)
- accidental injuries, reasons for any change in medication (drug and/or dose), reasons for any medical, nursing or pharmacy consultation, or reasons for admission to hospital or surgical procedures
- overdoses and medication errors with and without clinical consequences

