8.2.2 Recording of Adverse Events

The investigator must record all AEs in the AE log provided in each subject's eCRF with information about:

- AE
- date and time of onset (time can be omitted, if applicable)
- intensity
- causal relationship to IMP

- action taken to IMP
- other action taken
- date and time of outcome (time can be omitted, if applicable)
- outcome
- seriousness

Each of the items in the AE log is described in detail in the following sections.

Adverse Events

Adverse events should be recorded as diagnoses, if available. If not, separate signs and symptoms should be recorded. One diagnosis/symptom should be entered per record.

If a subject suffers from the same AE more than once and the subject recovers between the events, the AEs should be recorded separately. If an AE changes in intensity, a worst-case approach should be used when recording the event, i.e. the highest intensity and the longest duration of the event.^a

A procedure is not an AE; the reason for conducting the procedure is. Hospitalization is not an AE; the reason for hospitalization is. Death is not an AE, but the cause of death is (an exception is sudden death of unknown cause, which is an AE).

Date and Time of Onset

The date of onset is the date when the first sign(s) or symptom(s) were first noted. If the AE is an abnormal clinically significant laboratory test or outcome of an examination, the onset date is the date the sample was taken or the examination was performed.

Intensity

The intensity of an AE must be classified using the following 3-point scale:

Mild: awareness of signs or symptoms, but no disruption of usual activity

Moderate: event sufficient to affect usual activity (disturbing)

Severe: inability to work or perform usual activities (unacceptable)

^a Exception: if an AE with onset before the first IMP administration (i.e., a pre-treatment AE) changes in intensity, this must be recorded as 2 separate events. The initial AE should be recorded with outcome “not yet recovered” and the date and time of outcome are when the intensity changed. The second AE should be recorded with date and time of onset when the intensity changed.

Causal Relationship to IMP

The possibility of whether the IMP caused the AE must be classified as 1 of the following:

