9.8.3 Safety Laboratory Variables

Clinical laboratory variables will be presented in 2 ways. First, mean change from baseline to the end of the double-blind treatment visit will be summarized. Baseline will be defined as the last assessment before the first dose of IMP. Second, the number and percentage of subjects with

treatment-emergent potentially clinically significant laboratory values on or before the end of the double-blind treatment visit will be tabulated.

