2.2.2 Secondary endpoints

- The proportion of subjects in clinical remission at Months 2, 4, and 6, defined as a score of 0 for rectal bleeding and 0 or 1 for stool frequency based on Clinical Response Score subset of the Clinical and Endoscopic Response Score
- Time to relapse, defined as number of days from randomization to the day of withdrawal due to escalation of therapy (i.e., surgical therapy, use of steroids, immunosuppressive or immunomodulating drugs, biologics, increase dose of 5 aminosalicylic acid [5-ASA] in any form)
- The proportion of subjects with an increase from baseline in the Clinical and Endoscopic Response Score by 2 or more points in at least 1 component or by 1 or more points in at least 2 components at Month 6
- The change from baseline in serum CRP levels at Months 2, 4, and 6
- The change from baseline in fecal calprotectin levels at Months 2, 4, and 6
- The change from baseline to each scheduled assessment for published and validated domain scores of the IBDQ
- Safety assessed by incidence and severity of AEs and abnormal laboratory values

3 Trial design

This is a randomized, double-blind, placebo-controlled, parallel-group, multicenter, international, Phase 3 trial to investigate the safety and efficacy of mesalamine 2 g extended release granules (sachet) for maintenance of clinical and endoscopic remission in subjects with UC. Subjects who are in remission can be enrolled in the current trial via 1 of 3 pathways.

- Pathway 1: Subjects who are in remission following 8 weeks of double-blind treatment in Study 000174 can be randomized into Study 000175. The clinical and endoscopic remission criteria for Study 000174 include a Clinical and Endoscopic Response Score as a score of 0 for rectal bleeding and 0 or 1 with at least 1 point decrease from baseline for stool frequency, with an endoscopic score of 0 or 1.
- Pathway 2: Subjects in remission at the end of the 8-week open-label treatment period in Study 000174 will be allowed to be randomized into Study 000175.
- Pathway 3 – de novo: Subjects who did not participate in Study 000174 can also be enrolled; these subjects will have been treated with various medications for UC (excluding biologics and long-term [≥ 6 months] immunosuppressants) and will have been in remission for < 1 year. These de novo subjects will undergo a 72-hour mesalamine washout prior to entering the current trial and will have a Clinical and Endoscopic Response Score assessment to ensure eligibility.

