10.3.3 Markedly Abnormal Changes

Number and percentage of subjects who experienced at least one pre-specified markedly abnormal value ([Appendix 1](#)) during the treatment for each laboratory variable will be summarized by the baseline category (i.e., low, normal, high, absent, or present).

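### The laboratory shift table uses only the last on-treatment value, so smaller reversible abnormalities get no count by arm in the SAP text (minor)

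*SAP*

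**What the plan says.** SAP 2.2.2 lists as a secondary endpoint: "Safety assessed by incidence and severity of AEs and abnormal laboratory values". The laboratory outputs that serve it are in SAP 10.3, and SAP 10.1 makes safety summaries by treatment group.

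- **10.3.2, reference range.** "A shift table regarding the laboratory value category defined below will be created for baseline and end of treatment for each laboratory parameter". The categories are low, normal and high (absent or present for urinalysis). SAP 10.3 defines the second time point: "End of treatment will include the last post-baseline observation during the treatment period".
- **10.3.3, any time on treatment.** "Number and percentage of subjects who experienced at least one pre-specified markedly abnormal value" are summarized by baseline category, using the limits in Appendix 1, Table A 1.
- **10.3.1.** Descriptive statistics at Week 2 and Months 2, 4 and 6.
- **10.3.4.** Listings, by treatment group and site, of subjects with an abnormal value at any time.

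Protocol 9.8.3 asks for mean change to the end of double-blind treatment. Its only counts and percentages are for values of this kind: "treatment-emergent potentially clinically significant laboratory values on or before the end of the double-blind treatment visit will be tabulated".

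There is also an adverse event route. Protocol 7.1.7 has the investigator "evaluate and document whether the results are normal or abnormal and whether abnormal results are clinically significant". Protocol 8.1 counts as an adverse event "any laboratory abnormality, vital sign, or finding from physical (or gynecological) examination assessed as clinically significant by the investigator", and 8.2.2 adds: "The investigator must record all AEs in the AE log". SAP 10.2.2 then counts treatment-emergent events.

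**The concern.** The endpoint speaks of the incidence of abnormal laboratory values, and incidence calls for a count of subjects. The only count against the reference range looks at a single on-treatment value per subject, the last one. A rise that comes and goes between baseline and that test is tabulated as normal.

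What is at stake is narrow. A difference between mesalamine and placebo in, say, transient ALT or AST between 1 and 3 times the upper limit of normal (ULN) would not show as a count in any output the SAP text describes. A reader would have to count it by hand from the listings. The primary analysis and the efficacy conclusions do not depend on this.

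**Working it through.** The plan states no figure on this point, so there is none to reproduce. The check is mainly a comparison of texts, with some arithmetic for scale.

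**1. On-treatment tests per completer.** Protocol Table 1 and 6.2.3 to 6.2.5 give chemistry and hematology four (Week 2, Months 2, 4, 6), coagulation three (Months 2, 4, 6) and urinalysis one (Month 6). SAP 10.3.1 also reports all four visits. Protocol 7.1.7 differs: for blood tests on treatment it names only Visits 2 and 5, which would make two. Under either reading at least one test precedes the last, so the gap exists. Urinalysis has no earlier scheduled test and is unaffected.

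**2. Follow one value.** Take ALT at 2xULN at Month 2, normal at Month 6, not judged clinically significant.

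| Output | Treatment of this value | Subject counted as abnormal? |
|---|---|---|
| SAP 10.3.1 | Enters the Month 2 mean, median, minimum and maximum | No |
| SAP 10.3.2 | Normal at end of treatment | No |
| SAP 10.3.3, Table A 1 | Limit is above 3xULN | No |
| SAP 10.2.2 | Not an adverse event | No |
| SAP 10.3.4 | Listed by treatment group and site | No, listing only |

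**3. Width of the band.** The documents show no reference ranges, so the band between the range and the Table A 1 limit can be stated only for limits set in multiples of ULN:
- AST, ALT, GGT: above 1 and up to 3xULN.
- Total bilirubin: above 1 and below 1.5xULN.
- Alkaline phosphatase: above 1xULN, unless it is both above 3xULN and up 25% from baseline.

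For the other variables, INR and activated partial thromboplastin time included, the width is unknown.

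**4. What the shift table alone misses.** Suppose onset is equally likely at any of a subject's V tests and the abnormality spans L tests. The share back in range by the last test is max(V − L, 0)/V.
- V = 4: 3/4 = 75%, 2/4 = 50%, 1/4 = 25% for L = 1, 2, 3.
- V = 3: 2/3 = 67%, 1/3 = 33% for L = 1, 2.
- V = 2: 1/2 = 50% for L = 1, and 0% for L = 2.

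Early withdrawal reduces V and so lowers the share. An abnormality that persists to the last test is never missed. These are shares for one table, before removing what 10.3.3 and the adverse event tables catch.

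**5. Bias an any-time count could bring.** Assume no drug effect and an independent chance p of an out-of-range result at each test, so that any-time = 1 − (1 − p)^V. As an upper-end assumption, let every non-remitter withdraw, with an end-of-treatment test: 32% on mesalamine (100 − 68) and 51% on placebo (100 − 49), from the rates in SAP 3.2.
- Withdrawal in Days 0–14, 14–56, 56–112 and 112–168 gives 1, 2, 3 and 4 tests. Spread evenly over 168 days, the weights are 14/168 = 0.083, 42/168 = 0.250, 56/168 = 0.333 and 0.333.
- At p = 5%, 1 to 4 tests give 0.0500, 0.0975, 0.1426 and 0.1855. Completers: 0.1855. Evenly spread withdrawals: 0.1379.
- Mesalamine: 0.68 × 0.1855 + 0.32 × 0.1379 = 17.0%. Placebo: 0.49 × 0.1855 + 0.51 × 0.1379 = 16.1%. The difference is 0.9 points, about 1.2 subjects per 130.
- Extreme case, one test for every withdrawal: 0.68 × 0.1855 + 0.32 × 0.05 = 14.2% against 0.49 × 0.1855 + 0.51 × 0.05 = 11.6%. The difference is 2.6 points, about 3.3 subjects per 130.
- At p = 2% the two differences are 0.4 and 1.1 points.

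**The case against.** The strongest reply is that this is a preference, not an error. Protocol 9.8.3 sets the laboratory analysis and the SAP delivers it, with a shift table, by-visit statistics and listings added. Neither document promises an any-time count of every out-of-range value, and the endpoint does not define abnormal. The sponsor chose thresholds in Table A 1 and counts values beyond them at any time. What remains must meet four conditions at once and is still listed by arm. The related events named in protocol 1.3 include no laboratory signal. The shells are in a separate document (SAP 14) and may already hold the table. An any-time count would also pick up background noise and depend on withdrawal.

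Most of this stands, and it keeps the point small. A reader might infer that the SAP departs from the protocol; it does not. What does not answer the point is the appeal to the listings and by-visit statistics, because neither gives a number of subjects by arm. The SAP already goes beyond 9.8.3 by comparing values with the reference range, but does so at the one on-treatment time point that hides recovery. The withdrawal bias is small under the assumptions above and can be made visible.

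**Conclusion.** The gap is real, but closing it is a minor improvement. In the SAP text, a hematology, chemistry or coagulation value that is out of range before the last test, short of Table A 1, back in range at the last test and not judged clinically significant gets no number and percentage by arm.

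The number of subjects affected cannot be estimated, because the documents give no rates, durations or reference ranges. A reader might take the 75%, 50% and 25% shares as the proportion of transient abnormalities the plan loses. They are not: they describe the shift table alone, assume four tests and equally likely onset, and fall to 50% and 0% for one- and two-test abnormalities with two tests. A reader might also infer that large transient values go uncounted. Those reaching Table A 1 are counted at any time, and those judged clinically significant are adverse events. An abnormality still present at withdrawal is likely to be the last value, because the note to protocol Table 1 has all who discontinue complete end-of-treatment assessments.

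The conclusion rests on the SAP text only. If the shells already contain a worst-value shift, what is missing is one sentence.

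**What to change.** In SAP 10.3.2, for hematology, chemistry and coagulation, add a shift from baseline category to worst on-treatment category, with number and percentage by arm.

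- Show worst-low and worst-high separately, since one subject can have both.
- Include all baseline categories. Exclusion criterion 10 bars ALT or AST only from 3xULN upward, so some subjects may enter above the range.
- Say whether unscheduled results count. SAP 10.3.3 does not restrict its count to scheduled visits, and the same rule would be consistent.
- Keep the baseline-to-end-of-treatment shift, which shows recovery.
- Beside it, give low, normal and high counts by arm at each scheduled visit. That is enough to show whether unequal numbers of tests drive a difference; no further rate is needed.

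Leave 10.3.3 and the urinalysis shift as they are. It would also help to align protocol 7.1.7 with Table 1 and 6.2.3 to 6.2.5 on the blood-test visits.

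The cost is SAP wording and one extra set of tables from data already collected, with no new tests or visits. The downside is that any-time counts rise with the number of tests, so unequal withdrawal can bias them slightly, as sized above. The by-visit counts expose this but do not correct for withdrawal that is itself related to the laboratory value.

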10.3.3 Markedly Abnormal Changes

Number and percentage of subjects who experienced at least one pre-specified markedly abnormal value ([Appendix 1](#)) during the treatment for each laboratory variable will be summarized by the baseline category (i.e., low, normal, high, absent, or present).

10.3.4 Data Listings

Data listings will be prepared by treatment group and trial site for all subjects with any abnormal laboratory values at any time-point (including screening, baseline, and treatment period).

10.4 Vital Signs and ECG

10.4.1 Vital Signs

Baseline for all vital signs will be the values obtained at the last assessment prior to the first dose of IMP. Treatment-emergent vital signs data will include tests completed after the first dose of IMP. End of treatment will include the last post-baseline observation during the treatment.

10.4.1.1 Summary Statistics

Change and percentage change from baseline at end of treatment will be presented for each vital sign variable. In addition, descriptive statistics, i.e., the number of subjects with data, mean (standard deviation), median, minimum, and maximum values, will be presented for observed values and change/percentage change from baseline at baseline, Week 2, Months 2, 4, and 6 for each vital sign variable. The Weeks 2, Months 2, 4, and 6 measurements for the analysis will be identified based on the method described in Section [9.1](#).

10.4.1.2 Markedly Abnormal Changes

Number and percentage of subjects who experienced at least one pre-specified markedly abnormal value ([Appendix 1](#)) during the treatment for each vital sign variable will be summarized.

10.4.1.3 Data Listings

Data listings will be prepared by trial site for all subjects with any markedly abnormal vital sign values at any time-point (including screening, baseline, and treatment period).

10.4.2 ECGs

Baseline for all ECG variables will be the values obtained at the last assessment prior to the first dose of IMP. Treatment-emergent ECG data will include variables measured after the first dose of IMP. End of treatment will include the last post-baseline observation during the treatment period.

QTc will be calculated based on Bazett's (QTcB) and Fridericia's (QTcF) corrections.

$$QTcB[ms] = \frac{QT}{\sqrt{RR}}$$

$$QTcF[ms] = \frac{QT}{\sqrt[3]{RR}}$$

$$\text{where, } RR = \frac{60}{\text{Heart Rate}}$$

10.4.2.1 Summary Statistics

Change from baseline at end of treatment will be presented for each ECG variable. In addition, descriptive statistics, i.e., the number of subjects with data, mean (standard deviation), median, minimum, and maximum values, will be presented for observed values and change from baseline at baseline and Month 6 for each ECG variable. The Month 6 measurement for the analysis will be identified based on the method described in Section 9.1.

10.4.2.2 Markedly Abnormal Changes

Number and percentage of subjects who experienced at least one pre-specified markedly abnormal value (Appendix 1) during the treatment for each ECG variable will be summarized.

Tables, figures and listings shells will be presented in a separate document.

Appendix 1 Markedly Abnormal Laboratory Safety Values, Vital Signs and ECGs

Table A 1: Markedly abnormal Criteria for Laboratory Tests

Variable	Units	Markedly abnormal Criteria	
		Low	High
Haematology			
Haemoglobin	g/L	≤ 115	Not applicable
Haematocrit	Ratio	≤ 0.32	≥ 0.56
Total WBC	10 ⁹ /L	≤ 2.8	≥ 16.0
Eosinophils	%	Not applicable	≥ 10
Neutrophils	%	≤ 15	≥ 90
Lymphocytes	%	≤ 10	≥ 80
Monocytes	%	Not applicable	≥ 20
Basophils	%	Not applicable	≥ 5
Platelets	10 ⁹ /L	≤ 75	≥ 700
Total RBC	10 ¹² /L	≤ 3.5	Not applicable
Clinical Chemistry			
AST	IU/L	Not applicable	> 3xULN
ALT	IU/L	Not applicable	> 3xULN
Alkaline phosphatase	IU/L	Not applicable	> 3xULN and 25% increase from baseline
GGT	IU/L	Not applicable	> 3xULN
Total bilirubin	µmol/L	Not applicable	≥ 1.5xULN
Urea nitrogen	mmol/L	Not applicable	≥ 10.7
Creatinine	µmol/L	Not applicable	≥ 177
eGFR	mL/min	<30	Not applicable
Total protein	g/L	≤ 45	≥ 90
Albumin	g/L	≤ 25	≥ 65
Sodium	mmol/L	≤ 130	≥ 155
Potassium	mmol/L	≤ 3.0	≥ 5.8
Chloride	mmol/L	≤ 90	≥ 115
Calcium	mmol/L	≤1.8	≥ 3.9
Glucose	mmol/L	≤ 2.8	≥ 10
Coagulation			
INR		<0.8	>1.1
Activated partial thromboplastin time	Sec	Not applicable	>70

Table A 2: Markedly abnormal Criteria for Vital Signs*

Variable	Criterion Value	Change from Baseline
Systolic blood pressure	≥ 180 mmHg	Increase of ≥ 20 mmHg
	≤ 90 mmHg	Decrease of ≥ 20 mmHg
Diastolic blood pressure	≥ 105 mmHg	Increase of ≥ 15 mmHg
	≤ 50 mmHg	Decrease of ≥ 15 mmHg
Pulse rate	≥ 120 bpm	Increase of ≥ 15 bpm
	≤ 50 bpm	Decrease of ≥ 15 bpm
Body temperature		Increase to ≥ 39.4°C

* To be identified as markedly abnormal, a treatment value must meet the criterion value and also the specified change from baseline.

Table A 3: Abnormal Criteria for Quantitative ECG Data*

Variable	Abnormal Treatment-Emergent Value
ECG heart rate	≤ 50 bpm and decrease from baseline of ≥ 15 bpm
	≥ 120 bpm and increase from baseline of ≥ 15 bpm
Duration of PR interval	> 220 msec
Duration of QRS interval	> 120 msec
Duration of QTc interval	> 450 msec
Duration of QTc interval	> 480 msec
Duration of QTc interval	> 500 msec
Duration of QTc interval	Increase from baseline of ≥ 30 msec
Duration of QTc interval	Increase from baseline of ≥ 60 msec

* QTc will be calculated using both Bazett's and Fridericia's corrections.

